APPENDIX C
KARNOFSKY/LANSKY PERFORMANCE STATUS SCALE

Karnofsky Scale (recipient age ≥ 16 years)	Lansky Scale (recipient age ≥ 1 year and <16 years)
Able to carry on normal activity; no special care is needed	Able to carry on normal activity; no special care is needed
100 - Normal, no complaints, no evidence of disease	100 - Fully active
90 - Able to carry on normal activity	90 - Minor restriction in physically strenuous play
80 - Normal activity with effort	80 - Restricted in strenuous play, tires more easily, otherwise active
Unable to work, able to live at home, cares for most personal needs, a varying amount of assistance is needed	Mild to moderate restriction
70 - Cares for self, unable to carry on normal activity or to do active work	70 - Both greater restrictions of, and less time spent in active play
60 - Requires occasional assistance but is able to care for most needs	60 - Ambulatory up to 50% of time, limited active play with assistance/supervision
50 - Requires considerable assistance and frequent medical care	50 - Considerable assistance required for any active play, fully able to engage in quiet play
Unable to care for self, requires equivalent of institutional or hospital care, disease may be progressing rapidly	Moderate to severe restriction
40 - Disabled, requires special care and assistance	40 - Able to initiate quite activities
30 - Severely disabled, hospitalization indicated, although death not imminent	30 - Needs considerable assistance for quiet activity
20 - Very sick, hospitalization necessary	20 - Limited to very passive activity initiated by others (e.g., TV)
10 - Moribund, fatal process progressing rapidly	10 - Completely disabled, not even passive play

APPENDIX D
ANTHROPOMETRY (Height, Weight and BSA calculations)

**APPENDIX D:
Anthropometry (Height, Weight, and BSA calculations)**

Drug Dosing by Body Size

Drug dosing will be based on either body surface area (BSA) or body weight.

1. BSA is calculated in m². The formula by definition adjusts for both under and overweight individuals. The formula for this calculation is:

$$BSA (m^2) = \frac{\sqrt{\text{actual weight (kg)} \times \text{height (cm)}}}{60}$$

2. Body weight is measured in kg. The ideal body weight (IBW) will be calculated in the following ways:

Age ≥ 18 years

Gender (height)	
Male (>5ft)	50 kg + (2.3 kg/inch over 5 feet)
Female (>5ft)	45.5 kg + (2.3 kg/inch over 5 feet)
Subject <5ft	subtract 2.3 kg/inch
Rounding	Height in inches will be rounded to the nearest whole number
Height with inches < ½ inch	Round down to the nearest whole inch (e.g., 5ft 5 ¼ in will be rounded to 5ft 5 in)
Height with inches ≥ ½ inch	Round up to the nearest whole inch (e.g., 5ft 6 ½ in will be rounded to 5ft 7 in)

Age <18 years

Pre-pubertal males (<14 years) females (<12 years)	Ideal body weight (IBW) will be calculated by matching body weight at the 50th percentile for length-for-age or height-for-age at the 50th percentile CDC growth chart
Post-pubertal adolescents males (≥14 years) females (≥12 years)	Ideal body weight will be assessed using the body mass index (BMI). If the child’s normal BMI [body weight in kg/ height in meters ²] is between the 25-75th percentile on the CDC growth chart, the child may be considered at IBW
Adolescents whose BMI is > 75th percentile	Ideal body weight will be the 75th percentile BMI body weight
Adolescents whose BMI is < 25th percentile	Ideal body weight will be the 25th percentile BMI body weight

Note: When deviating from these age ranges (based on early or late maturity), the dietitian will document the rationale in the nutrition assessment.

Body Weight/Adjusted Body Weight for Drug Dosing

Adult and Pediatric Subjects:

Adjusted Body Weight will be calculated as follows:

$$\text{Ideal Body Weight} + 0.25 (\text{actual body weight} - \text{ideal body weight})$$

Body Weight Shifts After Initial Evaluation:

Individuals with significant body weight shifts after the initial evaluation will have the adjusted body weight reassessed by the study site's Clinical Nutrition Staff as appropriate.

APPENDIX E
LABORATORY ASSESSMENTS

APPENDIX E:

Protocol-Based Laboratory Procedures

There are three research laboratory studies associated with the BMT CTN 1904 clinical trial that are optional.

5. Treosulfan Pharmacokinetics (PK; Optional; Table 19)

Studies have demonstrated highly predictable PK in adult patients; however, limited data are available for pediatric patients. In addition, very little data is available on the relationship between Treosulfan exposure and HCT outcomes including early and late toxicities and engraftment. We plan on collecting PK samples on patients enrolled on this clinical trial in order to gain a better understanding of the relationship between the exposure to Treosulfan AUC to engraftment, transplant related mortality, overall and event-free survival for patients with BMFD. This information will help guide future studies using Treosulfan-based conditioning in patients with non-malignant diseases. This is an optional research study and Treosulfan PK data will not be used to adjust the patient's Treosulfan dose.

Treosulfan pharmacokinetic sampling and analysis on peripheral blood samples will be done on days -6 and -5. The same peripheral blood sample will be used for both Treosulfan and Treosulfan monoepoxide quantitation (samples will be split in PK Lab during analysis process). Peripheral blood samples (1 mL per sample) will be collected at 6 timepoints associated with both the day -6 and day -5 Treosulfan infusions. PK samples must be drawn from a different lumen/venous access than the drug infusion. If this is not possible and blood sampling needs to occur from the same lumen for Treosulfan infusion, document on the Treosulfan PK worksheet.

We will perform Treosulfan PK studies in approximately 5 patients for each of the following age groups: 1) 1 year to < 2 years, 2) 2 years to <4 years, 3) 4 years to <12 years and 4) \geq 12 years (total patients: approximately 20).

For patients who enroll in the Treosulfan PK, the following will be required:

- 1) Clinical sites will need to accurately record infusion dates, infusion start and end times, as well as the timing of the PK blood sample collections.
- 2) Patient height, weight, BSA (within 3 days of starting Treosulfan)
- 3) Serum hematocrit and creatinine will need to be drawn with the patient's morning labs (prior to the start of Treosulfan) on days -6 and -5.
- 4) Due to Treosulfan interpatient variability which may be dependent on the patient's fluid status, sites will be required to document the total fluids given to patients (IV plus po) from the time point of admission to the hospital for initiation of conditioning through 24 hours after the Treosulfan infusion has completed.
- 5) Treosulfan and the monoepoxide degrade rapidly. Collected blood must be immediately placed on ice, centrifuged within 30 minutes of collection, and placed at -20C or below within 1 hour of blood draw. Within 5 days of blood collection, frozen plasma should be stored at -70C or below until shipment.

PK sampling kits will be provided by the BMT CTN, and locally processed frozen plasma samples will be periodically batch-shipped directly to the Seattle Cancer Care Alliance (SCCA) Pharmacokinetics Lab for temporary storage and batched PK testing and analysis. Comprehensive instructions detailing Treosulfan infusion, PK blood sample collection, sample stabilization, blood

sample processing and batched frozen plasma sample shipping will be provided in the BMT CTN 1904 Research Sample Information Guide.

Table 19: PK Sample Collection Schedule for Day -6 and Day -5 Treosulfan Infusions		
Time Point	Collection Window	Blood Volume
Pre-infusion	Within 5 minutes before starting Treosulfan infusion	1 mL
End-of-infusion (EOI)	EOI + 5 minutes	1 mL
EOI + 20 minutes	+/- 5 minutes	1 mL
3.5 hours after start of infusion	+/- 10 minutes	1 mL
6 hours after start of infusion	+/- 10 minutes	1 mL
9 hours after start of infusion	+/- 10 minutes	1 mL

6. Biological Studies and Mutational Testing (Optional; Table 20)

Biological Studies

Recent attention has focused on genomic analysis of somatic mutations for risk stratification to inform treatments tailored to the individual patient. A subset of patients with BMFD are at high risk for regimen-related toxicities. In addition, a subset of patients with BMFD develop malignancies, predominantly solid tumors, post-HCT. Identification of patients at risk for these complications would allow appropriate adjustment of HCT regimens and institution of surveillance strategies for early tumor detection. Such genomic studies also stand to advance our understanding of the molecular pathogenesis of bone marrow failure to develop novel treatments.

The objective of the second laboratory correlate to this clinical trial will be to collect blood and/or marrow samples (if performed for clinical reasons) from consenting patients prior to the initiation of conditioning as well as around 1-year post-HCT. The goal of this research is to assess somatic genomic analysis of patients with severe bone marrow failure before and 1-year post-HCT, T-cell phenotypes, and comparison of cytokine levels before and after HCT. The objective is to identify risk factors associated with HCT complications. If samples have been donated and subject does not continue to transplant, samples will be stored for future research.

Mutational Testing

Over the past 5-10 years, there have been significant strides made in identifying new genetic mutations in patients with inherited BMFD. However, there remain a fair number of patients who are diagnosed with an underlying BMFD but lack a genetic mutation. One common reason is that commercial genetic panels are very different and do not analyze for all the known genetic mutations for these diseases. As has been mentioned above, a definite diagnosis is important for future management and surveillance of these patients. [name] of Cohen Children's Medical Center, in collaboration with [name] at the National Human Genome Research Institute, will analyze peripheral blood on patients who lack a genetic mutation, and perform whole exome or whole genome sequencing with the goal of identifying new mutations for patients with BMFD.

Table 20: Optional Research Study Samples					
Study Purpose	Sample Type	Sample Collection Summary	Sample Collection Time Points	Shipping Summary	Shipping Location
Biologic Studies	Bone Marrow Aspirate 8-10 mL (if a clinical marrow occurs)	Collect bone marrow aspirate sample and place: 
 • 5 mL into a green top plastic BD Vacutainer® tube containing sodium heparin anticoagulant. • 3-5 mL into a lavender top plastic BD Vacutainer® tube containing EDTA anticoagulant. 	Pre-transplant Within 60 days prior to enrollment Post-transplant Day 365 post-HCT	Blood and marrow samples will be shipped at ambient temperature on the day of collection to the TransLab project laboratory by priority overnight FedEx delivery for processing and research testing. Detailed instructions for specimen collection, handling, and shipment to TransLab will be provided in the BMT CTN 1904 Research Sample Information Guide.	TransLab Boston Children's Hospital
	Peripheral Blood 8-10 mL	Collect peripheral blood sample and place: 
 • 5 mL into a green top plastic BD Vacutainer® tube containing sodium heparin anticoagulant. • 3-5 mL into a lavender top plastic BD Vacutainer® tube containing EDTA anticoagulant. 			
Mutational Testing	Peripheral Blood 10 mL For Patients <30 kg 20 mL For Patients ≥30 kg	Collect peripheral blood sample and place into one or more lavender top plastic BD Vacutainer® tubes containing EDTA anticoagulant.	Pre-transplant Prior to the initiation of conditioning	Blood samples will be shipped at ambient temperature on the day of collection to the [name]/NHGRI laboratory by priority overnight FedEx delivery for processing and research testing. Detailed instructions for specimen collection, handling, and shipment to the [name]/NHGRI lab will be provided in the BMT CTN 1904 Research Sample Information Guide.	[name] Laboratory National Human Genome Research Institute

APPENDIX F
DIAGNOSIS AND SEVERITY SCORING FOR ACUTE GVHD

Harris (MAGIC) Criteria

GVHD Target Organ Staging⁶⁷

Stage	Skin (active erythema only)	Liver (total bilirubin)	Upper GI	Lower GI (stool output/day)
0	No active (erythematous) GVHD rash	< 2 mg/dl	No or intermittent nausea, vomiting or anorexia	Adult: < 500 ml/day or <3 episodes/day Child: < 10 ml/kg/day or <4 episodes/day
1	Maculopapular rash <25% BSA	2–3 mg/dl	Persistent nausea, vomiting or anorexia	Adult: 500–999 ml/day or 3–4 episodes/day Child: 10–19.9 ml/kg/day or 4–6 episodes/day
2	Maculopapular rash 25 – 50% BSA	3.1–6 mg/dl	-	Adult: 1000–1500 ml/day or 5–7 episodes/day Child: 20 – 30 ml/kg/day or 7–10 episodes/day
3	Maculopapular rash > 50% BSA	6.1–15 mg/dl	-	Adult: >1500 ml/day or >7 episodes/day Child: > 30 ml/kg/day or >10 episodes/day
4	Generalized erythroderma (>50% BSA) plus bullous formation and desquamation > 5% BSA	>15 mg/dl	-	Severe abdominal pain with or without ileus, or grossly bloody stool (regardless of stool volume).

Overall clinical grade (based upon most severe target organ involvement):

- Grade 0: No stage 1–4 of any organ
- Grade I: Stage 1–2 skin without liver, upper GI or lower GI involvement
- Grade II: Stage 3 rash and/or stage 1 liver and/or stage 1 upper GI and/or stage 1 lower GI
- Grade III: Stage 2–3 liver and/or stage 2–3 lower GI, with stage 0–3 skin and/or stage 0–1 upper GI
- Grade IV: Stage 4 skin, liver, or lower GI involvement, with stage 0–1 upper GI

Categories of Acute and Chronic GVHD

Categories of Acute and Chronic GVHD			
Category	Time of Symptoms after HCT	Presence of Acute GVHD Features	Presence of Chronic GVHD Features
Acute GVHD			
Classic acute GVHD	≤ 100 d	Yes	No
Late-onset acute GVHD	> 100 d	Yes	No
Chronic GVHD			
Classic chronic GVHD	No time limit	No	Yes
Overlap syndrome	No time limit	Yes	Yes

APPENDIX G
DIAGNOSIS AND SEVERITY SCORING FOR CHRONIC GVHD

(2014 NIH Consensus Criteria⁶²)

	SCORE 0	SCORE 1	SCORE 2	SCORE 3
PERFORMANCE SCORE:  KPS ECOG LPS	 Asymptomatic and fully active (ECOG 0; KPS or LPS 100%)	 Symptomatic, fully ambulatory, restricted only in physically strenuous activity (ECOG 1, KPS or LPS 80-90%)	 Symptomatic, ambulatory, capable of self-care, >50% of waking hours out of bed (ECOG 2, KPS or LPS 60-70%)	 Symptomatic, limited self-care, >50% of waking hours in bed (ECOG 3-4, KPS or LPS <60%)
SKIN† SCORE % BSA  GVHD features to be scored by BSA:	 No BSA involved	 1-18% BSA	 19-50% BSA	 >50% BSA
SKIN FEATURES SCORE:	 No sclerotic features		 Superficial sclerotic features "not hidebound" (able to pinch)	Check all that apply:  Deep sclerotic features  "Hidebound" (unable to pinch)  Impaired mobility  Ulceration
Other skin GVHD features (NOT scored by BSA) Check all that apply:  Hyperpigmentation  Hypopigmentation  Poikiloderma  Severe or generalized pruritus  Hair involvement  Nail involvement  Abnormality present but explained entirely by non-GVHD documented cause (specify): _____				
MOUTH Lichen planus-like features present:	 No symptoms	 Mild symptoms with disease signs but not limiting oral intake significantly	 Moderate symptoms with disease signs with partial limitation of oral intake	 Severe symptoms with disease signs on examination with major limitation of oral intake
 Abnormality present but explained entirely by non-GVHD documented cause (specify): _____				

Organ scoring of chronic GVHD. ECOG indicates Eastern Cooperative Oncology Group; KPS, Karnofsky Performance Status, Lansky Performance Status; BSA, body surface area; ADL, activities of daily living; LFTs, liver function tests; AP, alkaline phosphatase; ALT, alanine aminotransferase; ULN, normal upper limit. *Weight loss within 3 months. Skin scoring should use both percentage of BSA involved by disease signs and the cutaneous features scales. When a discrepancy exists between the percentage of total body surface (BSA) score and the skin feature score, OR if superficial sclerotic features are present (Score 2), but there is impaired mobility or ulceration (Score 3), the higher level should be used for the final skin scoring. To be completed by specialist or trained medical providers. **Lung scoring should be performed using both the symptoms and FEV1 scores whenever possible. FEV1 should be used in the final lung scoring where there is discrepancy between symptoms and FEV1 scores.

	SCORE 0	SCORE 1	SCORE 2	SCORE 3
EYES	 No symptoms	 Mild dry eye symptoms not affecting ADL (requirement of lubricant eye drops ≤ 3 x per day)	 Moderate dry eye symptoms partially affecting ADL (requiring lubricant eye drops > 3 x per day or punctal plugs), WITHOUT new vision impairment due to KCS	 Severe dry eye symptoms significantly affecting ADL (special eyewear to relieve pain) OR unable to work because of ocular symptoms OR loss of vision due to KCS
Keratoconjunctivitis sicca (KCS) confirmed by ophthalmologist:				
	 Yes  No  Not examined			
 Abnormality present but explained entirely by non-GVHD documented cause (specify):				
GI Tract	 No symptoms	 Symptoms without significant weight loss* ($< 5\%$)	 Symptoms associated with mild to moderate weight loss* (5-15%) OR moderate diarrhea without significant interference with daily living	 Symptoms associated with significant weight loss* $> 15\%$, requires nutritional supplement for most calorie needs OR esophageal dilation OR severe diarrhea with significant interference with daily living
Check all that apply:				
	 Esophageal web/proximal stricture or ring  Dysphagia  Anorexia  Nausea  Vomiting  Diarrhea  Weight loss $\geq 5\%*$  Failure to thrive			
 Abnormality present but explained entirely by non-GVHD documented cause (specify):				
LIVER	 Normal total bilirubin and ALT or AP < 3 x ULN	 Normal total bilirubin with ALT ≥ 3 to 5 x ULN or AP ≥ 3 x ULN	 Elevated total bilirubin but ≤ 3 mg/dL or ALT > 5 ULN	 Elevated total bilirubin > 3 mg/dL
 Abnormality present but explained entirely by non-GVHD documented cause (specify):				
LUNGS**				
Symptom score:	 No symptoms	 Mild symptoms (shortness of breath after climbing one flight of steps)	 Moderate symptoms (shortness of breath after walking on flat ground)	 Severe symptoms (shortness of breath at rest; requiring O ₂)
Lung score:	 FEV1 $\geq 80\%$	 FEV1 60-79%	 FEV1 40-59%	 FEV1 $\leq 39\%$
% FEV1 				
Pulmonary function tests				
	 Not performed			
 Abnormality present but explained entirely by non-GVHD documented cause (specify):				

	SCORE 0	SCORE 1	SCORE 2	SCORE 3
JOINTS AND FASCIA P-ROM score (see below) Shoulder (1-7): ____ Elbow (1-7): ____ Wrist/finger (1-7): ____ Ankle (1-4): ____	 No symptoms	 Mild tightness of arms or legs, normal or mild decreased range of motion (ROM) AND not affecting ADL	 Tightness of arms or legs OR joint contractures, erythema thought due to fasciitis, moderate decrease ROM AND mild to moderate limitation of ADL	 Contractures WITH significant decrease of ROM AND significant limitation of ADL (unable to tie shoes, button shirts, dress self etc.)
 Abnormality present but explained entirely by non-GVHD documented cause (specify):				
GENITAL TRACT (See Supplemental figure[†])  Not examined Currently sexually active  Yes  No	 No signs	 Mild signs [†] and females with or without discomfort on exam	 Moderate signs [†] and may have symptoms with discomfort on exam	 Severe signs [†] with or without symptoms
 Abnormality present but explained entirely by non-GVHD documented cause (specify):				
Other indicators, clinical features or complications related to chronic GVHD (check all that apply and assign a score to severity (0-3) based on functional impact where applicable none – 0, mild -1, moderate -2, severe – 3)				
 Ascites (serositis) ____  Myasthenia Gravis ____  Pericardial Effusion ____  Peripheral Neuropathy ____  Eosinophilia > 500/ μ l ____  Pleural Effusion(s) ____  Polymyositis ____  Platelets <100,000/ μ l ____  Nephrotic syndrome  Weight loss>5%* without GI symptoms  Others (specify):				
Overall GVHD Severity (Opinion of the evaluator)  No GVHD  Mild  Moderate  Severe				

APPENDIX H
QUALITY OF LIFE QUESTIONNAIRE USING THE PATIENT REPORTED
OUTCOMES MEASUREMENT INFORMATION SYSTEM (PROMIS)

QOL Study Design

The following instruments will be used to assess QOL within one month before transplant (Baseline), at 180 days and 1-year post-transplant. Only English- or Spanish-speaking trial participants aged 5 years and older will be included in the QOL collection. Patients aged 8-17 at the time of assessment will complete pediatric instruments. Proxy reports (e.g., parents,guardians) will be collected for patients aged 5 to 8.

At the Baseline time point, center or CIBMTR staff will administer QOL instruments electronically or on paper. At 180 day and 1 year time points, the CIBMTR will administer the QOL surveys electronically or on paper, per respondent need or preference. Each time point will take about 2-3 minutes to complete.

PROMIS Global

The PROMIS Global measure contains 10 items for adults and 9 items for pediatric patients (self- or proxy-report), with two summary scores for physical and mental functioning. The median score is 50 with a standard deviation of 10. Higher scores indicate better QOL⁶⁸.

Subject/Patient Reported Outcomes (PRO)

This includes all items/questions included on each patient- or proxy-reported QoL survey.

PROMIS Scale – Global Health (adult self-report)

Please respond to each question or statement by marking one box per row

	Excellent	Very good	Good	Fair	Poor
In general, would you say your health is:					
In general, would you say your quality of life is:.					
In general, how would you rate your physical health?					
In general, how would you rate your mental health, including your mood and your ability to think?					
In general, how would you rate your satisfaction with your social activities and relationships?					
In general, please rate how well you carry out your usual social activities and roles. (This includes activities at home, at work and in your community, and responsibilities as a parent, child, spouse, employee, friend, etc.)					

	Complet ely	Mostly	Moderate ly	A little	Not at all
To what extent are you able to carry out your everyday physical activities such as walking, climbing stairs, carrying groceries, or moving a chair?					

In the past 7 days...	Never	Rarely	Sometime s	Often	Always
To what extent are you able to carry out your everyday physical activities such as walking, climbing stairs, carrying groceries, or moving a chair?					

In the past 7 days...	None	Mild	Moderate	Severe	Very severe
How would you rate your fatigue on average?					

In the past 7 days...											
How would you rate your pain on average?											
	0	1	2	3	4	5	6	7	8	9	10
	No pain										Worst pain imaginable

PROMIS Scale – Global Health (pediatric self-report)

Please respond to each question or statement by marking one box per row

	Excellent	Very good	Good	Fair	Poor
In general, would you say your health is:					
In general, would you say your quality of life is:					

	Excellent	Very good	Good	Fair	Poor
In general, how would you rate your physical health?					
In general, how would you rate your mental health, including your mood and your ability to think?					

	Never	Rarely	Sometimes	Often	Always
How often do you feel really sad?					

	Always	Often	Sometimes	Rarely	Never
How often do you have fun with friends?					
How often do your parents listen to your ideas?					

In the past 7 days...	Never	Almost Never	Sometimes	Often	Always
I got tired easily					
I had trouble sleeping when I had pain					

PROMIS Scale – Global Health (pediatric parent proxy report)

Please respond to each question or statement by marking one box per row

	Excellent	Very good	Good	Fair	Poor
In general, would you say your child’s health is:					
In general, would you say your child’s quality of life is:.					
In general, how would you rate your child’s physical health?					
In general, how would you rate your child’s mental health, including your mood and your ability to think?					

	Never	Rarely	Sometime s	Often	Always
How often does your child feel really sad?					

	Always	Often	Sometime s	Rarely	Never
How often does your child have fun with friends?					
How often does your child feel that you listen to his or her ideas?					

In the past 7 days...	Never	Almost Never	Sometime s	Often	Always
My child got tired easily					
My child had trouble sleeping when he/she had pain					

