Blood and marrow samples will be obtained within 60 days prior to enrollment for somatic genomic analyses, T-cell phenotypes, and cytokine measurement. Those providing consent will have blood (3mL-5mL EDTA tube and 5mL in sodium heparin tube) and marrow samples (3mL-5mL in EDTA tube and 5mL in sodium heparin tube) sent to the central laboratory for these studies. A CBC with differentials is required to be done on the same day as the sample collection. This can be done in conjunction with standard of care tests. (**Appendix E**) If samples have been donated and subject does not continue to transplant, samples will be stored for future research.

3. Mutational Testing (Optional) – Baseline assessment

Individuals who have participated in previous genetic studies and who have no identified mutation will be eligible to participate in this whole exome/genome sequencing study (excluding patients with PNH). Those interested in participation will be asked to provide peripheral blood (10 or 20 ml, based on subject’s weight) in EDTA (purple top) tubes for DNA extraction after informed consent for whole exome/genome sequencing is obtained. (**Appendix E**)

4. Health Related Quality of Life (Optional): Baseline assessment

At the time a patient is identified as participating in the study, the CIBMTR Survey Research Group (SRG) is notified and then adds that patient to CIBMTR's electronic Patient Reported Outcomes (ePRO) system for long-term QOL tracking.

Pre-transplant (baseline) QOL data will be collected by the center or CIBMTR electronically or on paper forms within 30 days prior to HCT. If conditioning is delayed, the QOL surveys should be repeated so the QOL surveys are completed within 30 days prior to HCT. Electronically collected baseline QOL surveys will be directly entered in the ePRO system by the patient or proxy. The center will securely email, or fax baseline QOL instruments completed on paper to the SRG for entry into the ePRO system. (**Appendix H**)

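### As printed in Appendix H, the adult PROMIS form holds 9 distinct items against the 10 stated, and the proxy mental-health item mixes the child with the respondent

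*Protocol*

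**What the plan says.** Appendix H presents its forms as the instruments to be used at baseline, day 180 and 1 year, on screen or on paper. It gives their length: "The PROMIS Global measure contains 10 items for adults and 9 items for pediatric patients", the latter figure covering both self-report and proxy report, "with two summary scores for physical and mental functioning". It also says of the printed content: "This includes all items/questions included on each patient- or proxy-reported QoL survey".

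On the adult form, "To what extent are you able to carry out your everyday physical activities such as walking, climbing stairs, carrying groceries, or moving a chair" is printed with answers from Completely to Not at all. The same text is printed again directly below, under a past-7-days heading, with answers from Never to Always.

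The parent proxy form asks: "In general, how would you rate your child’s mental health, including your mood and your ability to think".

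Section 5.8.2 plans means and standard deviations of the total and subdomain scores at three time points, with paired t-tests and linear mixed models for change from baseline. Sections 2.2.2 and 3.3.4 make this endpoint exploratory and optional.

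On timing, Section 4.3.3 has baseline data collected "electronically or on paper forms within 30 days prior to HCT". Appendix H likewise allows one month before transplant.

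**The concern.** A question that asks about extent cannot sensibly be answered with a frequency. The second printing has its own recall period and its own response scale, so it looks as though another item belongs in that row and was overwritten by a copy of the row above. A site that follows the printed form would then never ask that item. Its recall period is 7 days, so the answer could not be collected reliably later. The scores planned for adults would rest on an instrument one item short of the one described.

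On the proxy form, the clause about mood and ability to think keeps the self-report pronoun. A parent may take it to mean the child, themselves or both, and different parents may read it differently.

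The baseline window raises a lesser and separate question. It runs up to the transplant, and conditioning starts on day -6, so a baseline could be answered after treatment has begun.

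**Working it through.** The check is a count of the printed rows and of the distinct question texts on each form in Appendix H, set against the stated numbers of items. No sample-size or power formula is involved.

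| Form | Rows, by block of response options | Rows | Distinct items | Stated |
|---|---|---|---|---|
| Adult self-report | 6 + 1 + 1 + 1 + 1 | 10 | 10 - 1 = 9 | 10 |
| Pediatric self-report | 4 + 1 + 2 + 2 | 9 | 9 | 9 |
| Parent proxy | 4 + 1 + 2 + 2 | 9 | 9 | 9 |

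The adult blocks are six items from Excellent to Poor, one from Completely to Not at all, one from Never to Always, one on fatigue and one on pain. The stated 10 is reproduced as a count of rows but not as a count of items. Both stated 9s are reproduced.

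**Adult row.** The two printings have identical wording. The first carries a scale of degree, which fits. The second carries a scale of frequency over the past 7 days, which does not. The document does not say which item should stand there.

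**Proxy item.** The mental-health item begins by asking about the child and ends by referring to the respondent. The other eight proxy items ask about the child throughout. The clause matches the self-report wording, so it appears to have been carried over unchanged. The item is still present, so the count of 9 holds; the fault is in what it refers to.

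**Effect on scoring.** Appendix H names two summary scores but gives no key linking items to scores. Section 5.8.2 adds a total score that Appendix H does not define. The documents therefore show that 1 of 10 adult items is not asked on the printed form, but not which score it feeds.

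**Baseline window.** Of the 30 permitted days before transplant, days -6 to -1 fall in the conditioning schedule (Table 1), which leaves 30 - 6 = 24 days clear of it. The adult fatigue and pain items look back 7 days, so an answer given on day -1 would cover all the days on which conditioning is given.

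**After correction.** With the right item in the Never to Always row, the adult form has 10 rows and 10 distinct items, as stated. Correcting the proxy pronouns leaves that form at 9. No sample size, power or error rate changes.

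**The case against.** The best reply is that this is a fault in a printed appendix, not a demonstrated loss of data. Electronic surveys run in the CIBMTR system (Section 4.3.3), and CIBMTR collects the later assessments online or, on request, on paper (Section 4.3.4). The live build is not shown and may be correct. Scoring keys and rules for missing items usually sit in an analysis plan or instrument manual, neither of which is at hand. Nine adult items are still collected. The proxy item can still be answered and scored. The adults concerned may also be few: in the earlier marrow-failure cohort of Section 1.3.4 the median age was 15 years (range 1.2 to 22).

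Much of this stands, and it rules out several stronger readings that a reader might infer:

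- That the planned quality-of-life summaries cannot be produced at all. The pediatric self-report form is intact and the proxy form can still be scored.
- That every adult has lost an item at all three assessments. This assumes that the printed form is what was administered, which the document does not show.
- That the proxy item asks about the parent instead of the child. Its main clause is about the child; only the qualifying clause strays.

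The reply does not remove the point. Appendix H says that it contains all items and that these instruments will be used, and paper is allowed at each time point, so a site following the protocol would use the faulty form. A text-extraction fault cannot be fully excluded, but the second printing keeps its own heading and scale and the neighbouring rows read cleanly.

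On the baseline window, Table 13 has a Baseline column separate from days -6 and -5 and marks the survey only in the former. Section 4.3.3 also asks for a repeat if conditioning is delayed, which suggests that a survey before conditioning is intended. A reader might infer that change scores will be biased towards improvement. The schedule does not direct a survey during conditioning, and no figure in the document supports a bias of any size.

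**Conclusion.** Wrong as written, within an optional exploratory endpoint. The printed adult form contradicts its own description: 9 distinct items against 10, with one row whose scale does not fit its question. The printed proxy form has 1 of 9 items with a mixed reference.

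The consequence is conditional. If these forms are administered as printed, the adult measure cannot be scored as the 10-item instrument described, and the validity of the proxy item is weakened. Which adult summary score suffers, and whether a usable score could still be formed from the remaining items, cannot be shown from the document. The primary endpoint, sample size and safety monitoring are unaffected.

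The wording of the baseline window is loose rather than harmful. It is a minor point and does not depend on the questionnaire errors.

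**What to change.** 1. Reprint the adult Never to Always row and the proxy mental-health item in Appendix H from the source instrument.
2. Check the live electronic version and the paper forms, in both English and Spanish, against that instrument, and record which version has been administered.
3. If the faulty adult form has been used, state before analysis how records lacking the displaced item will be scored, or that the affected score will not be reported for those records.
4. Word the baseline window in Section 4.3.3 and Appendix H as within 30 days before, and completed before, the first dose of conditioning, in line with the Baseline column of Table 13.

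The cost is an editorial amendment and one check of the forms in use. No visits or assessments are added and no sample-size figure changes.
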